Ipilimumab will be administered intravenously over 90 ± 10 minutes after the DLI product observation period is completed, and dosing will continue in 3-week intervals for 4 cycles, unless unacceptable toxicity or symptomatic disease progression occurs (see Appendices E-F for disease progression criteria). MTD will be assessed at day 43 by DLT criteria as defined in **Section 5.4**. At their day 92 evaluation, patients without evidence of progressive disease or unacceptable toxicity can receive maintenance Ipilimumab **per their assigned dose level** on a q 3 monthly basis starting from week 24, for 4 doses.

5.1.5 Dose-escalation/De-escalation schema: Four dose-level combinations of CD25/Treg-depleted DLI plus Ipilimumab will be evaluated to determine MTD.

Table 4: CD25/Treg-depleted DLI plus Ipilimumab Dose Escalation/De-escalation Schema Per Cohort

Cohort	Viable CD3+ Dose (#cells/kg*)	Ipilimumab Dose
Dose Level +2	3×10^7	10 mg/kg
Dose Level +1	3×10^7	3 mg/kg
Dose Level 0	3×10^7	1 mg/kg
Dose Level -1	1×10^7	1 mg/kg

** Recipient's body weight in Kg

** Acceptable range: $0.8-1 \times 10^7$ viable CD3+ cells/kg for DL -1; $2.5-3 \times 10^7$ viable CD3+ cells/kg for DL 0, +1, and +2

To ensure at least 3 patients will be evaluable within a group, a cohort of 5 eligible patients will enter at each dose level. If there are fewer than 3 evaluable patients in a cohort, additional patients will be added at that dose-level. Patients may be enrolled in the next cohort when 3 or more evaluable patients from the previous cohort have completed their day 43 assessment. Patients will be considered unevaluable for the determination of MTD if they require removal from the study due to alternative treatments for progressive disease (except hydroxyurea, with PI approval) or other reasons not related to an adverse event within 6 weeks after initial dosing. Additional patients may be enrolled at a specific dose cohort to substitute for patients within the cohort who are considered unevaluable for MTD. **There will be at least one-week interval between consecutive enrollments at the same dose level during phase 1A.**

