Dose escalation or de-escalation is as follows: If ≤ 1 DLTs are observed within a cohort of up to 5 evaluable patients at dose level 0, then a dose escalation will take place. If ≤ 1 DLTs are observed at dose-level -1 or dose-level +2, this dose will be the MTD. If ≥ 2 DLTs are observed in a cohort of up to 5 evaluable patients, then the MTD is considered exceeded. If this is dose level 0, dose de-escalation will take place, and up to 5 patients will be enrolled at dose level -1. If ≥ 2 DLTs are observed at dose level +2, then dose level +1 will be the MTD. If ≥ 2 DLTs are observed at dose level -1, accrual will stop.

CONFIDENTIAL

This document is confidential. Do not disclose or use except as authorized.

5.1.7 Further Therapy for Patients with Progressive Disease: Treatment with hydroxyurea to temporarily control counts, with PI approval, will be acceptable on study. Patients who require additional therapy due to progressive disease will come off study to be treated at the discretion of the treating physician. Patients who receive off-study therapy (e.g. chemotherapy) will be followed for 1 year following DLI infusion for survival outcomes. Phase 1a patients who are removed from study without evidence of toxicity prior to their week 6 assessment (e.g. for progressive disease) will be considered unevaluable for MTD assessment, and will be replaced as necessary. **There will be at least one-week interval between consecutive enrollments at the same dose level during phase 1A.**

5.1.7 Phase 1b: In phase Ib, an additional 10 patients will be enrolled at the MTD to better define toxicity and describe preliminary efficacy at this dose level. No patients will be replaced in this phase.

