11. MEASUREMENT OF EFFECT / CLINICAL RESPONSE

Evaluable for toxicity- Participants who receive cell infusion at the specified dose plus Ipilimumab will be evaluated for toxicity. Evaluable patients are those who experience a DLT before day 43, or are assessable for DLT at day 43. Phase 1a patients who are unevaluable for DLT may be replaced.

Evaluable for response- Only those participants who have measurable disease present at baseline, have received cell infusion at the specified dose and least two cycles of Ipilimumab therapy, and have had their disease re-evaluated will be considered evaluable for response. These participants will have their response classified according to the disease-specific definitions stated in **Appendices E-F**. Patients unevaluable for response will not be replaced.

Response Criteria will be disease-specific, and are provided in detail in the following appendices:

- **Appendix E:** Acute Myelogenous Leukemia
- **Appendix F:** Myelodysplastic Syndrome / Myeloproliferative Neoplasm

Evaluation of Best Overall Response The best overall response is the best response recorded from the start of the treatment until disease progression/recurrence (taking as reference for progressive disease the smallest measurements recorded since the treatment started). The participant's best response assignment will depend on the achievement of both measurement and confirmation criteria

Duration of overall response: The duration of overall response is measured from the time measurement criteria are met for CR or PR (whichever is first recorded) until the first date that recurrence or PD is objectively documented, taking as reference for PD the smallest measurements recorded since the treatment started.

Duration of overall complete response: The duration of overall CR is measured from the time measurement criteria are first met for CR until the first date that recurrent disease is objectively documented.

Progression-Free Survival (PFS) is defined as the duration of time from start of treatment to time of objective disease progression or death whichever occurs first.

Overall Survival (OS) is defined as the duration of time from start of treatment to time of death.

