13.3 Secondary endpoints

- ORR (To determine complete remission (CR/CRi) rate at 6 weeks (day 43) after the cell infusion plus Ipilimumab)
- To determine the rate of progression-free survival (PFS) and overall survival (OS) at ~3 months (day 92) post cell infusion plus Ipilimumab
- To determine the rate of progression-free survival (PFS) and overall survival (OS) at ~ 1-year (60 weeks) post cell infusion plus Ipilimumab
- To determine the incidence and severity of acute GVHD rates after cell infusion plus Ipilimumab
- To determine the incidence and severity of chronic GVHD rates after cell infusion plus Ipilimumab

CONFIDENTIAL

This document is confidential. Do not disclose or use except as authorized.

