13.7 Analysis plan

Due to limited sample size, the analysis will be primarily descriptive. AEs/SAEs will be summarized by patient, type and grade as defined by the CTCAE v4.0. Rates will be described as proportions with exact binomial confidence intervals. CR/CRI rate at day 43 also will be described as a proportion with exact binomial confidence interval. Kaplan-Meier models will be used to estimate PFS and OS at day 100 and 1 year with exact pointwise confidence intervals. Acute and chronic GVHD will be described as cumulative incidence in the competing risks framework treating death without GVHD as a competing event. The association between clinical outcomes (response, PFS and OS and acute or chronic GVHD) and correlative endpoints (e.g., circulating Teff and Treg cells, number of AML/MDS/MPN blasts and other characteristics of the BM microenvironment pre-therapy and at post-treatment relapse) will be explored using univariable Cox, Fine and Gray regression analysis or exact Wilcoxon-Rank-Sum test, as appropriate. Analyses will be carried out in SAS 9.4 or R 3.3.2 or higher.

CONFIDENTIAL

This document is confidential. Do not disclose or use except as authorized.

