-Subjects who fail to achieve CR, Cri, or PR and who do not have criteria for PD will be defined as having the stable disease. If the subject dies prior to response assessment at the end of Cycle 1, then they will be classified as “indeterminate”.

E.1.7 Progressive disease (PD): may be defined as ONE of the following:

- $> 50\%$ increase in peripheral blood or bone marrow blasts from best assessment with minimum threshold of 20% blasts in the marrow or $1.0 \times 10^9/L$ blasts in peripheral blood.

-Development of biopsy proven extramedullary leukemia (if the subject has extramedullary

CONFIDENTIAL

This document is confidential. Do not disclose or use except as authorized.

disease at baseline, then PD will be defined by blood and marrow criteria or if new sites of extramedullary disease appear).

-If subject who present with an initial marrow blast percentage sufficiently high to preclude the ability to base disease progression on a >50% increase in marrow blast percentage, disease progression should be based on peripheral blood criteria or development of extramedullary leukemia as above.

E.1.8 Persistent Disease

Hematologic Persistence – Bone marrow or peripheral blasts >5% after d+30 following HCT

CONFIDENTIAL

This document is confidential. Do not disclose or use except as authorized.

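### The only response-evaluable set the plan defines requires two ipilimumab cycles and a re-evaluation; used as the day-43 CR/CRi denominator, it would drop early treatment failures and raise the rate

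*Combined protocol and SAP*

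**What the plan says.** Section 11 of the combined protocol and SAP sets four conditions for being evaluable for response: measurable disease at baseline, the specified cell dose, at least two ipilimumab cycles, and a disease re-evaluation. The middle two read: "have received cell infusion at the specified dose and least two cycles of Ipilimumab therapy". The rule is exclusive, and it is these participants whose response is classified under Appendices E and F. It adds: "Patients unevaluable for response will not be replaced".

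The endpoint in Section 13.3 is the "complete remission (CR/CRi) rate at 6 weeks (day 43) after the cell infusion plus Ipilimumab", with no two-dose condition. Section 13.7 says only that the "CR/CRI rate at day 43 also will be described as a proportion with exact binomial confidence interval". It does not say which patients form the denominator.

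Three other places bear on who reaches two cycles and a re-evaluation:

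- Section 1.1 puts the second ipilimumab dose on day 22. Table 6 schedules the first post-baseline marrow on day 43.
- Section 5.1.4 continues ipilimumab "unless unacceptable toxicity or symptomatic disease progression occurs". The Section 5.1 paragraph on further therapy says: "Patients who require additional therapy due to progressive disease will come off study".
- For AML, Appendix E.1.6 states: "If the subject dies prior to response assessment at the end of Cycle 1, then they will be classified as" indeterminate. It does not say whether that counts as a non-response.

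**The concern.** Whether a patient meets the two-cycle and re-evaluation conditions depends partly on how treatment goes. Someone with symptomatic progression in the first three weeks, someone who leaves the study for other therapy in that time, or someone who dies before day 22 never gets dose 2. Someone who gets dose 2 but dies before the day-43 marrow may never be re-evaluated. Under Section 11 none of these patients is evaluable for response, and nothing in the plan counts them as non-responders. A denominator that loses patients because they failed gives a rate that is too high.

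Phase 1b enrols 10 patients partly to describe preliminary efficacy, so one or two such losses would be visible in the reported percentage. Patients unevaluable for response are not replaced. A reader of the results would also find it hard to set the rate beside the earlier cell-only study in Section 2.2.1, where the 60% response at the same cell dose is 9 of all 15 patients at that level. That figure includes one PR and some patients without active disease at infusion, so the comparison is loose in any case.

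**Working it through.** The plan states no target, power or sample size for CR/CRi, so there is no figure of its own to reproduce. The check has two parts: what the text implies, and how far the rate could move.

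**Text.** Section 11 is the only place that defines a response population. Section 13.7 gives a proportion without a denominator. Section 13.3 dates the endpoint from cell infusion plus ipilimumab. The likely reading is that the Section 11 set will be used, but this is an inference.

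**Inputs.** Phase 1b has 10 patients (Section 5.1). Dose level 0 has 5 evaluable patients from phase 1a (Section 13.4, December 2020 amendment) and is the expansion dose (June 2021 amendment), so 5 + 10 = 15 at that level. The number lost (k) and the number in CR/CRi (x) are not in the documents. They are assumed here, with k from 0 to 2. It is also assumed that all N patients have measurable disease and that none of the k is in CR/CRi at day 43.

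**Formula.** Rate with everyone counted: x/N. Rate in the evaluable set: x/(N-k). Ratio: N/(N-k), whatever x is.

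- N = 10: 10/9 = 1.11 for k = 1; 10/8 = 1.25 for k = 2.
- N = 15: 15/14 = 1.07 for k = 1; 15/13 = 1.15 for k = 2.

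**Rates, with Clopper-Pearson 95% intervals.**

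| N | x | k = 0 | k = 1 | k = 2 |
|---|---|---|---|---|
| 10 | 2 | 20.0% (2.5-55.6) | 22.2% (2.8-60.0) | 25.0% (3.2-65.1) |
| 10 | 3 | 30.0% (6.7-65.2) | 33.3% (7.5-70.1) | 37.5% (8.5-75.5) |
| 10 | 5 | 50.0% (18.7-81.3) | 55.6% (21.2-86.3) | 62.5% (24.5-91.5) |
| 15 | 5 | 33.3% (11.8-61.6) | 35.7% (12.8-64.9) | 38.5% (13.9-68.4) |

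With no early losses there is no effect. With two, the rate rises by 7.5 points for 3/10 and by about 5 points for 5/15. Every shifted rate lies inside the interval for the all-counted rate in the same row.

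**The case against.** The strongest reply is that the exclusion is not actually written. Section 13.7 never invokes the Section 11 set, so the documented fault is an unnamed denominator. That is right, and it is why the point is conditional. A reader might infer that the plan says outright that early failures are left out of the CR/CRi rate; it does not. But no other response set exists, so an analyst following the document would probably use this one.

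A second reply is that E.1.6 gives early deaths a category, which suggests they stay in the analysis and simply are not CR/CRi. This carries some weight. However, the clause covers AML only, concerns deaths before an end-of-cycle-1 assessment for which Table 6 schedules no marrow, and does not say how the label is counted.

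Third, it is legitimate in a small descriptive study to ask how often patients with minimal exposure respond. That supports reporting the two-cycle set, but not leaving it as the only one with no rule for early failures.

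Fourth, early failures show up elsewhere: PFS and OS run from start of treatment, and Section 5.8 tracks survival and disease status for all patients. This stands and limits the harm, though it does not correct the CR/CRi rate itself.

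A reader might also take the cohort rule, "To ensure at least 3 patients will be evaluable within a group, a cohort of 5 eligible patients will enter at each dose level", as a sign that 40% of patients could be lost before dose 2. The documents do not support that. The allowance concerns DLT evaluability over six weeks, covers removal for reasons other than progression, and under Section 13.4 includes patients given off-dose cell products. Some patients lost in that window would already have had dose 2.

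**Conclusion.** The concern holds as a minor, conditional point. If the Section 11 set is the denominator, the day-43 CR/CRi rate leaves out patients because treatment failed and is biased upward by a factor of N/(N-k). For one or two losses that is 1.11 or 1.25 among the 10 expansion patients, and 1.07 or 1.15 among 15 at dose level 0. These sizes rest on assumed counts; the documents give no frequency of early loss, and with none the effect is nil. They also assume that none of the lost patients is in CR/CRi at day 43.

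The shifts are small beside the exact intervals, the endpoint is secondary and descriptive, and no decision rule in Section 13.4 uses it. A reader might infer that the efficacy picture as a whole, or the dose decision, is compromised. It is not: PFS and OS count these patients from start of treatment, and DLT and MTD have their own evaluability rules.

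**What to change.** In Sections 11 and 13.7, make the primary denominator for day-43 CR/CRi all patients with measurable baseline disease who received the specified cell dose and the first ipilimumab dose. Count as a non-responder anyone without a documented CR/CRi at the day-43 assessment, whether the reason is early progression, death (including AML patients labelled indeterminate under E.1.6), toxicity, withdrawal or a missing assessment. A patient who missed dose 2 but has a documented CR/CRi at that assessment then counts as a responder. Keep the two-cycle evaluable set as a sensitivity analysis, and give the number excluded with reasons.

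The cost is a few sentences. No visits, tests or patients are added, and Section 13.4 does not change. The downside is a slightly lower reported rate that includes some patients who had only one ipilimumab dose.

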12. DATA REPORTING / REGULATORY REQUIREMENTS

Adverse event lists, guidelines, and instructions for AE reporting can be found in Section 7.0 (Adverse Events: List and Reporting Requirements).

CONFIDENTIAL

This document is confidential. Do not disclose or use except as authorized.

12.1 Data Reporting

12.1.1 Method

The Office of Data Quality (ODQ) will collect, manage, and perform quality checks on the data for this study.

Note: If your study has been assigned to CDUS-Complete reporting, **all** adverse events (both routine and expedited) that have occurred on the study and meet the mandatory CDUS reporting guidelines must be reported via the monitoring method identified above. If your study has been assigned to CDUS-Abbreviated reporting, no adverse event reporting (routine or expedited) is required to be reported via CDUS.

12.1.2 Responsibility for Data Submission

Investigative sites within DF/HCC or DF/PCC are responsible for submitting data and/or data forms to the Office of Data Quality (ODQ) in accordance with DF/HCC policies.

12.2 Data Safety Monitoring

The DF/HCC Data and Safety Monitoring Committee (DSMC) will review and monitor toxicity and accrual data from this study. The committee is composed of medical oncologists, research nurses, pharmacists and biostatisticians with direct experience in cancer clinical research. Information that raises any questions about participant safety will be addressed with the Overall PI and study team.

The DSMC will review each protocol up to four times a year with the frequency determined by the outcome of previous reviews. Information to be provided to the committee may include: up-to-date participant accrual; current dose level information; DLT information; all grade 2 or higher unexpected adverse events that have been reported; summary of all deaths occurring within 30 days of intervention for Phase I or II protocols; for gene therapy protocols, summary of all deaths while being treated and during active follow-up; any response information; audit results, and a summary provided by the study team. Other information (e.g. scans, laboratory values) will be provided upon request.

12.3 Collaborative Agreements Language

Not applicable

13. STATISTICAL CONSIDERATIONS

CONFIDENTIAL

This document is confidential. Do not disclose or use except as authorized.

13.1 Study Design

This is an open-label, single center phase 1 study with the primary objective of establishing the safety and exploring the efficacy of infusing CD25/Treg-depleted cells plus Ipilimumab in AML, MDS and MPN patients who relapse after 8/8 HLA-matched donor hematopoietic cell transplant.

13.2 Primary endpoints

The primary endpoint of this study is to determine the maximum tolerated dose (MTD) of CD25/Tre-depleted DLI followed by Ipilimumab in AML, MDS and MPN patients relapsed after HLA-matched donor stem cell transplantation.

13.3 Secondary endpoints

- ORR (To determine complete remission (CR/CRi) rate at 6 weeks (day 43) after the cell infusion plus Ipilimumab)
- To determine the rate of progression-free survival (PFS) and overall survival (OS) at ~3 months (day 92) post cell infusion plus Ipilimumab
- To determine the rate of progression-free survival (PFS) and overall survival (OS) at ~ 1-year (60 weeks) post cell infusion plus Ipilimumab
- To determine the incidence and severity of acute GVHD rates after cell infusion plus Ipilimumab
- To determine the incidence and severity of chronic GVHD rates after cell infusion plus Ipilimumab

CONFIDENTIAL

This document is confidential. Do not disclose or use except as authorized.

13.4 Determining MTD

Four escalating/de-escalating doses of the combination therapy will be considered to determine the MTD: CD25/Treg depleted DLI 3×10^7 CD3⁺ cells/kg + Ipilimumab 10 mg/kg (Dose level +2), CD25/Treg depleted DLI 3×10^7 CD3⁺ cells/kg + Ipilimumab 3 mg/kg (Dose level +1), CD25/Treg depleted DLI 3×10^7 CD3⁺ cells/kg + Ipilimumab 1 mg/kg (Dose level 0, starting level), and CD25/Treg depleted DLI 1×10^7 CD3⁺ cells/kg + Ipilimumab 1 mg/kg (Dose level -1). Considering the DLT observation period of 6 weeks and the accrual rate, the study will enroll 5 eligible patients at each dose level to minimize delays in accrual. Patients will be unevaluable for MTD if they receive DLI product with cells not meeting the dose-level criteria (**Section 5.1.3**), die of progressive disease without DLT, or have disease progression or other reason requiring removal from the study without DLT within the 6 week DLT observation period (**Section 5.4**).

Since the MTDs of CD25/Treg depleted DLI and Ipilimumab were previously defined in monotherapy studies. Dose level 0 will be the initial dose level for this combination therapy. To ensure at least 3 patients will be evaluable in each dose level, a cohort of 5 eligible patients will enter at each dose level. If there are fewer than 3 evaluable patients in a cohort, additional patients can be added at that dose level. At any dose level, if 2 or more patients experience DLT, MTD is considered exceeded. If this is dose level -1, then the study will be terminated. If this is dose level +1 or +2, the next lower level (dose level 0 or +1, respectively) will be declared to be the MTD. If this is dose level 0, dose de-escalation will take place (decision rule I). If no DLT is seen in the first 3, 4, or 5 evaluable patients at dose level 0 or +1, then dose escalation will take place. If no DLT is seen in the first 3, 4, or 5 evaluable patients at dose level -1 or +2, that dose level will be declared to be the MTD. If there are 3 evaluable patients in a cohort of 5 eligible patients and if 1 of the 3 evaluable patients experiences DLT then 2 additional evaluable patients will be treated at the same dose level. If 1 or more of the 2 additional patients experience(s) DLT then MTD is considered to have been exceeded, and the decision rule I will be applied. If there are 4 evaluable patients and if 1 of the 4 evaluable patients experiences DLT then 1 additional evaluable patient will be treated at the same dose level. If this additional patient experiences DLT then MTD is considered to have been exceeded, and the decision rule I will be applied. If 1 DLT is seen in a total of 5 evaluable patients treated at dose level 0, then dose escalation will take place. If 1 DLT is seen in a total of 5 evaluable patients treated at dose level -1 or +2, then this dose level will be declared to be the MTD. **Table 8** shows the probability of escalation under various true DLT rates for the cohort. With this design, there is 92-93% probability of dose escalation if the true rate of DLT is 10% and 74-76% probability if the true DLT rate is 20%. Of note, the probability of dose de-escalation is one minus the probability of dose escalation.

Table 8. Probability of dose escalation

True rate of DLT	Prob. of Escalation for (3+2) evaluable cases	Prob. of Escalation for (4+1) evaluable cases	Prob. of Escalation for 5 evaluable cases
10%	0.926	0.919	0.919
20%	0.758	0.737	0.737

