CD25/Treg depletion: All cell processing will be performed at the DFCI cGMP CMCF (Connell O'Reilly Cell Manipulation Core Facility). Upon receipt of sufficient donor leukapheresis product from the donor center, the product will be selectively depleted of CD25^{hi} Treg cells using the ClinIMACS® CD25 Reagent System according to manufacturer's instructions. A detailed protocol for the preparation and use of the ClinIMACS® CD25 reagent is provided to the clinical site in the ClinIMACS® User Manual. Samples of the donor leukocyte preparation will be removed prior to processing and after completion of the CD25^{hi} cell depletion. These samples will be used to determine cell viability, and enumerate the CD3+, CD4+, CD8+, CD14+, CD20+, CD25+, CD45+, CD56+, CD127+, and FOXP3+ cells (in combination as necessary, e.g. CD4+CD25^{hi}FOXP3+ cells) before and/or after processing. Gram stain, endotoxin and sterility testing will also be performed on the donor leukocyte preparation. The CD25^{hi} depleted product will be denoted as 'TC-T Reg (CD25^{hi}) reduced cells'. **Release criteria are indicated in Table**

1. Product will be infused even if the final CD3+ cell dose/kg is below target at the maximum number of cells available after requisite QC samples obtained.

If the total product collected contains <1.5-fold excess of CD3+ cells/kg per planned infusion dose, the product will NOT undergo CD25^{hi} depletion, and the unmanipulated product will be given to the patient, per institutional standards of care. The patient will not be assessable for the study objectives, and will be replaced by another patient.

If the total product collected contains ≥ 1.5 -fold excess of CD3+ cells/kg per planned infusion dose, then the product will be CD25^{hi} depleted with the ClinIMACS CD25 device according to manufacturer instructions. After depletion, the volume of processed product infused will be adjusted to the targeted CD3+ cell dose per the dose level schema, while maintaining $\leq 0.5\%$ CD4+CD25^{hi} cells. There will be no add back of the depleted fraction enriched for CD4+CD25^{hi} cells.

If the composition of the product after processing cannot meet both targets above, then the volume infused will be adjusted to best target their CD3+ dose per dose-level cohort. The patient will be unevaluable for DLT assessment.

CONFIDENTIAL

This document is confidential. Do not disclose or use except as authorized.

Table 1: Product Release Criteria

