Test Performed	Test Method	Release Criteria
Viable CD3+ cell dose*	Flow Cytometry	Dose Level +2: 3×10^7 /kg Dose Level +1: 3×10^7 /kg Dose Level 0: 3×10^7 /kg Dose Level -1: 1×10^7 /kg
CD4+ CD25 ^{hi} cells	Flow cytometry	$\leq 0.5\%$ of viable lymphocytes
Viability	Trypan blue	$\geq 70\%$
Endotoxin	Charles River Endosafe® -PTS™ System	< 5.0 EU/Kg/hr
Gram stain	BWH Microbiology laboratory	No organisms

* Acceptable range: $0.8-1 \times 10^7$ viable CD3+ cells/kg for DL -1; $2.5-3 \times 10^7$ viable CD3+ cells/kg for DL 0, +1, +2

Donor Lymphocyte Infusion: The donor lymphocyte product will not be administered until it has passed the release criteria for infection control monitoring, as defined by the DFCI CMGTL and the FDA (**Table 1**). If release criteria (except CD3+ cell dose and CD4+CD25^{hi} cell fraction) are not met, the DLI product will NOT be infused, and the patient will be unevaluable for DLT assessment and will be replaced.

Once release criteria have been met, the DLI product will be infused into the recipient through a central or peripheral venous catheter, per the cell infusion SOP. The donor lymphocytes will be infused over 5-15 minutes. Acetaminophen 650mg PO and diphenhydramine 25mg IV or PO will be given as premedication prior to the infusion. Patients will be monitored for infusional reactions for 1 hour after the end of the infusion. Excess product, if any, will be cryopreserved per standard operating procedure for future use if necessary.

CD25/Treg-depleted DLI Dose Schema: Patients will receive a defined dose of CD25^{hi} Treg depleted DLI. 5 patients will be enrolled, initially at dose level 0, and subsequent cohorts will be dose adjusted per the CD3+ dose escalation/de-escalation schema detailed below.

Table 2: CD25/Treg-depleted DLI Dose Escalation/De-escalation Schema Per Cohort

Cohort	Viable CD3+ Dose* (#cells/kg)**
Dose Level +2	3×10^7
Dose Level +1	3×10^7
Dose Level 0	3×10^7
Dose Level -1	1×10^7

** Recipient's body weight in Kg

** Acceptable range: $0.8-1 \times 10^7$ viable CD3+ cells/kg for DL -1; $2.5-3 \times 10^7$ viable CD3+ cells/kg for DL 0, +1, and +2

CONFIDENTIAL

This document is confidential. Do not disclose or use except as authorized.

5.1.4 Ipilimumab administration.

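### A DLT after an off-target cell product can drop out of the MTD and Phase 1b counts, because that exclusion lacks the no-DLT limit placed on the other exclusions

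*Combined protocol and SAP*

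**What the plan says.** Section 13.4 lists who does not count toward the MTD. The first reason is the cell product: "Patients will be unevaluable for MTD if they receive DLI product with cells not meeting the dose-level criteria". The remaining reasons each exclude only patients who had no DLT: those who "die of progressive disease without DLT, or have disease progression or other reason requiring removal from the study without DLT" within the six-week window.

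Section 5.1.3 covers the same patients. A CD3+ shortfall does not stop treatment: "Product will be infused even if the final CD3+ cell dose/kg is below target". If the processed product cannot meet both the CD3+ target and the 0.5% ceiling on CD4+CD25hi cells, the volume is set to come as close as possible to the CD3+ dose, and "The patient will be unevaluable for DLT assessment". No exception is made for a DLT that has occurred. The text after Table 1 exempts these same two criteria from the rule that a failed release test blocks infusion. No section withholds ipilimumab from these patients.

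Section 11 gives two definitions in succession. The first is "Participants who receive cell infusion at the specified dose plus Ipilimumab will be evaluated for toxicity". The next sentence makes anyone with a DLT before day 43 evaluable and does not mention the product.

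Under Section 13.4, two DLTs at a level mean the MTD is exceeded. In Phase 1b, at most two DLTs among 10 evaluable patients make the dose the recommended Phase II dose, and three or more halt accrual. The Phase 1b paragraph (the second numbered 5.1.7) allows no replacement.

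**The concern.** The exclusion treats two different patients alike. One who received less than the assigned cell exposure and had no DLT says little about the assigned level, so leaving that patient out is sound. One who received less and still had a DLT generally counts against the level. Both are removed.

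Three features of the plan support this.

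- **CD3+ misses are shortfalls.** Under Section 5.1.3, "the volume of processed product infused will be adjusted to the targeted CD3+ cell dose per the dose level schema", and the acceptable ranges (2.5-3 and 0.8-1 x 10^7/kg) stop at the nominal dose. The step from level 0 to level -1 lowers only the cell dose, so the design itself takes fewer cells to be safer.
- **CD4+CD25hi misses mean more of those cells.** Section 2.2.1 reports an inverse relation between circulating Tregs and GVHD.
- **Levels 0, +1 and +2 share one cell dose and differ only in ipilimumab** (Table 4). An off-target patient is still due the full assigned dose of the escalated drug, and Section 5.4 counts toxicity related to either component.

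The primary endpoint and the Phase II dose recommendation rest on small counts, so losing one DLT matters whenever the count is at a boundary.

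**Working it through.** **1. The plan's own figures.** For five evaluable patients, P(escalate) = (1-p)^5 + 5p(1-p)^4. At p = 30% this is 0.528 and at 40% it is 0.337, as in Table 8. All 18 entries of Table 8 reproduce; the largest gap is 0.0015 (0.189 printed, 0.1875 exact, at 50%). Table 8 covers evaluable patients only, so it gives no weight to DLTs after off-target products.

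For the expansion, exact P(at most 2 DLTs in 10) is 0.930 at a 10% rate and 0.167 at 40%. Section 13.4 prints 0.07 and 0.83, which are the probabilities of 3 or more. That labelling error is a separate matter; the exact values are used below.

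**2. Assumptions.** The documents do not say how often products miss target. Let s be the share of off-target products (assumed 5-20%) and p the true DLT rate (10-40%), with equal risk in off-target patients. Phase 1a replacement is ignored.

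**3. Chance that at least one DLT is dropped:** 1 - (1 - sp)^n.

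- n = 5: from 1 - 0.995^5 = 0.02 to 1 - 0.92^5 = 0.34.
- n = 10: from 1 - 0.995^10 = 0.05 to 1 - 0.92^10 = 0.57.

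**4. Chance that the decision changes.** The count over all treated patients is Bin(n, p) and the on-target count is Bin(n, p(1-s)). The decision changes when the first reaches the threshold t and the second does not: P(Bin(n, p(1-s)) < t) - P(Bin(n, p) < t).

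| n, t | p | s | On-target count below t | Full count below t | Change |
|---|---|---|---|---|---|
| 5, 2 | 10% | 5% | 0.926 | 0.919 | 0.01 |
| 5, 2 | 20% | 10% | 0.778 | 0.737 | 0.04 |
| 5, 2 | 40% | 20% | 0.488 | 0.337 | 0.15 |
| 10, 3 | 10% | 5% | 0.938 | 0.930 | 0.01 |
| 10, 3 | 20% | 10% | 0.737 | 0.678 | 0.06 |
| 10, 3 | 30% | 20% | 0.556 | 0.383 | 0.17 |
| 10, 3 | 40% | 20% | 0.331 | 0.167 | 0.16 |

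**5. If off-target patients are at lower risk.** Suppose exactly two of 10 Phase 1b patients are off-target and p = 40%. With their DLTs dropped, P(at most 2) = P(Bin(8, 0.4) <= 2) = 0.315. With their DLTs counted it is 0.167 at equal risk and 0.237 at half the risk. The direction holds and the gap narrows.

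**6. What has happened so far.** Section 13.4 records three patients treated at level 0 and two more added to reach five evaluable, so 3 + 2 = 5 and none was excluded there. Level +1 is reported as one DLT in six patients. Level +2 was closed after its first patient had a fatal DLT.

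**The case against.** The strongest reply is that the plan does not speak with one voice. The second sentence of Section 11, read alone, counts any patient with a DLT before day 43, and the exceeded-MTD rule in Section 13.4 refers to patients, not evaluable patients. Sections 5.1.5 and 5.1.7 confine unevaluability to removals without toxicity, although they deal with removals and not with products. This stands to the extent that exclusion is not the only possible reading. It does not settle the matter, because Sections 13.4 and 5.1.3 address the off-target patient directly and exclude without condition. The choice between readings could then be made after a DLT is known.

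Second, limiting the MTD set to patients who received the specified product is defensible, and a product that fails depletion is arguably not the product under test. That supports excluding patients without a DLT. It is weaker for DLTs, particularly those caused by ipilimumab.

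Third, a reader might infer that these are the most informative toxicities in the trial. The documents do not support that: DLTs include immune-related events, cytopenias and infusion reactions, the Treg evidence concerns GVHD and autoimmunity, and Section 2.1 describes CD25hi cells as including Tregs, not as consisting only of them.

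Fourth, the events are not lost. They are reported (Section 7.7) and summarised (Section 13.7), and the DSMC may receive DLT information (Section 12.2). The team also acted beyond the formal count: it closed level +2 after one DLT and moved from level +1 to level 0 partly because of late events. A reader might infer that such a DLT counts for nothing, or that conduct always leans toward acceptance; neither follows. The effect is confined to the formal tally.

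Finally, the requirement to collect at least 1.5 times the planned CD3+ dose may keep shortfalls uncommon. The documents give no rate.

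**Conclusion.** The point holds as a defect in the counting rule. As written in Sections 13.4 and 5.1.3, a real DLT can leave the MTD and Phase II dose counts because of the cell product, and the text that would keep it, in Section 11, conflicts with them. The tilt in the formal tally is toward acceptance.

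Its size rests on assumptions. With a 5-20% off-target share, true DLT rates of 10-40% and equal risk, the decision changes with probability about 0.01-0.15 in five patients and 0.01-0.17 in ten; lower risk in off-target patients would shrink this. A reader might take the chance of at least one off-target product, 1 - (1-s)^n, as the size: 0.23-0.67 in five patients and 0.40-0.89 in ten. That overstates it, because a DLT must also occur in such a patient, and it changes the decision only when the count is at the boundary.

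The documents do not show that any DLT was dropped. With five evaluable patients reported at level 0 and the expansion proceeding there, the live effect is mainly on the Phase 1b count.

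**What to change.** - In Section 13.4, attach the no-DLT limit to the product clause: a patient whose infused product was outside the CD3+ range or above the CD4+CD25hi limit is unevaluable, and replaceable in Phase 1a, only if no DLT occurs in the 42-day window. A DLT counts at the assigned level in both phases.
- Make Section 5.1.3 and both sentences of Section 11 say the same.
- State whether the Phase 1b rule is applied to 10 treated or 10 evaluable patients, since no one is replaced.
- Check whether any patient already treated with an off-target product had a DLT, and re-tally if so.

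The cost is one clause in three places and a check of existing data. The downside is that the DLT count can only become slightly less favourable, and it will include DLTs that followed a product not fully to specification. Such cases can be flagged in the report.
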